**CINCINNATI CHILDREN’S HOSPITAL MEDICAL CENTER
INSTITUTIONAL REVIEW BOARD – Protocol**
and
Community Health Center, Inc IRB
Protocol Template (HRP-212)

1) Protocol Title

Rx for Success: A Randomized Controlled Trial of Technology-Based Dialogic Reading Training Incorporated Into Reach Out and Read

2) Principal Investigators

Overall: [name], MS MD FAAP
Cincinnati Children’s Hospital Medical Center
Division of General and Community Pediatrics
Reading and Literacy Discovery Center

On-site at CHC: [name], MD
Community Health Center at Connecticut Children’s Hospital

Other staff: [name] (coordinator, CCHMC), [name] MD (co-I, CCHMC), [name], PhD (consultant, Reach Out and Read National Office (MA)), [name] (consultant, Children, Inc.). A primary research coordinator will be hired to conduct this study at the primary care clinical site in CT.

3) Funding Source

The Carol Ann and Ralph V. Haile, Jr./U.S. Bank Foundation
The Grossman Family Foundation

4) Objectives*

Specific Aim 1 (Rx for Success; RS): To explore the efficacy of incorporating dialogic reading training via the RS application into ROR during well-child visits for infants (6-12 months old) and toddlers (18-24 months old), compared to standard ROR practice.

Hypothesis 1a (language): Language scores (LENA Snapshot) will be higher in children whose caregivers are provided with the RS app.

Hypothesis 1b (social-emotional): Social-emotional development scores (DECA-I/T items) will be higher in children whose caregivers are provided with the RS app.

Hypothesis 1c (dialogic quality): Dialogic reading quality scores (DialogPR-I/T) will be higher in caregivers presented with the RS app.

Hypothesis 1d (attitudes): Attitudes towards shared reading at home (items from StimQ-P READ and PVR) will be higher in families provided with the RS app.

Specific Aim 2 (exploratory):

Hypothesis 2a: Reported screen-based media use (ScreenQ) will be lower in families provided with the RS app, reflecting greater emphasis on interactive shared reading.

Hypothesis 2b: Language (LENA Snapshot) and social-emotional (DECA-I/T items) scores will be higher for children with less reported screen-based media use (ScreenQ).

5) Background*

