Overview/Rationale: Our strategy is to conduct an innovative experiment that is achievable within 15 months, providing data for a larger, longer-term longitudinal study exploring the impact of “enhanced” ROR on home reading environment and cognitive and social-emotional development. This study involves a low-SES population of infants and toddlers at-risk for adverse cognitive and social-emotional outcomes, during a foundational period of early brain development, who stand to benefit from effective early intervention to improve the quality of cognitive stimulation and nurturing in the home. Such innovation is needed, given challenges to providing consistent, effective dialogic reading training in busy clinical settings, where such at-risk families are uniquely accessible. The resources and infrastructure are in place via ROR for this work to commence expeditiously with high probability of success.

Preliminary data: A pilot process evaluation field test of 26 predominantly African-American and Urban Appalachian low-income families enrolled in ROR, demonstrated an overwhelmingly positive response to the RS app with 100% of participants rating the video as motivational and 95% rating the reminders as helpful. Quotes from participants included:

“The video talked about singing and when I did that she seemed to really like it and become engaged.”

“My grandson loves it. He’s really interested and we are happy to get the reminders.”

“We all know that it’s important to read to your child, but we don’t always remember every day....having the reminders helped me to actually do the reading more.”

A separate pilot study involving ROR families found that those who already knew about the importance of reading aloud considered videos incorporated into the RS app to be valuable in explaining how to read more interactively with their young children. By contrast, a recent MRI-based study involving video observations of 22 low-SES mothers

reading with their preschool-age children found low verbal interactivity and engagement despite prior access to home visiting and ROR, suggesting a need for improved dialogic training.²⁰

Other recent work that will support this proposed project includes initial validation of brief measures assessing shared/dialogic reading quality (DialogPR) and screen-based media use in the home (ScreenQ).⁴⁶

6) Setting of the Human Research

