Study Design: This is a prospective, randomized controlled trial involving 2 age categories of low-SES caregiver-child dyads served by the ROR program, each followed for 6 months. For each category, a baseline assessment (pre-) and an outcomes assessment (post-) will be conducted, to explore effects of “enhanced” ROR using the RS app. Category 1 will involve 6 month-old infants, followed until they are 12 months old. Category 2 will involve 18 month-old toddlers, followed until they are 24 months old. Recruitment, informed consent, behavioral testing and intervention will take place at a high-volume primary care clinic based in a major, urban academic medical center in Connecticut (Community Health Center, Inc. at Connecticut Children’s Medical Center; CHC@CCMC). Providers in the clinical sites are trained in child development and the administration of ROR during well-child visits between birth and age 5, including those involved with our study at 6, 12, 18, and 24 months old.

A graphic of our study design is provided in **Figure 1** below. Families assigned to the control arm in each age category will receive customary ROR, including the provision of an age-appropriate children’s book, and reading-related developmental surveillance and anticipatory guidance. In addition, control families will receive a new children’s book reinforcing AAP screen-based media recommendations.⁴⁸ Families in the intervention arm in both age categories will receive “enhanced” ROR involving the provision of the **Rx for Success** (RS) application at the baseline visit (6 months old and 18 months old, respectively). No additional intervention will take place, other than text messages and other content built into the RS application.

a) Recruitment Methods

Sample Size/Power Analysis: Via our CRC, we will recruit 248 children in 2 age categories: approximately 6 months old (infants, n=124), and approximately 18 months old (toddlers, n=124) via convenience sampling in the CHC@CCMC clinic waiting room

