during regularly scheduled well-child visits. This study will be powered based on the primary language outcome measure (LENA Snapshot). For a two-group (intervention/control), pre-post repeated-measure analysis with two age categories (6-12 months, 18-24 months), an ANCOVA model will be applied for both age categories and their interaction, to assess the difference in language scores between intervention and control groups. For this study, at least 180 subjects will be needed to have 80% statistical power to detect slightly greater than medium effect size (Cohen $f=0.30$), controlling for the baseline pre-measurement with a two-sided significance level of 0.05. This effect size was determined considering the 2008 National Early Literacy Panel Report, which examined 16 studies and reported an effect size of 0.6 for dialogic reading on language outcomes ($d=0.6$; Shanahan, et al).⁴⁹ A separate meta-analysis of 18 studies that tested dialogic reading intervention found average effect size for language outcomes and vocabulary of 0.29 and 1.02, respectively.⁸ However, these reports largely involved preschool- and school-age children, and no studies to our knowledge have reported effect sizes of dialogic reading for language in infants and toddlers.

We anticipate that full enrollment for this study within 6 months is feasible given historical well-visit volumes for these ages (40/month meeting enrollment criteria) at the participating clinic at CHC@CCMC. The CRC will optimize enrollment efficiency factoring scheduled well-visit volumes and demographic needs (age), via weekly communication regarding clinic schedules with clinic managers. The CRC will identify the arrival and registration of potential participants by monitoring the daily schedule (in Centricity) to identify well child visits for children of the appropriate age groups, and will greet them in the waiting room. For enrolled patients only, the CRC will also monitor scheduled encounters (in e-Clinical Works) to identify upcoming appointments for the follow-up (post-intervention) visit, and will monitor arrival in Centricity. The CRC will approach families in the waiting area, confirm that the child meets inclusion criteria by age, and present the major aims of the study in plain language:

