“We are conducting a research study looking at how different ways of providing tips about reading with young children affects attitudes towards reading and early child development. This will involve a little extra time at today’s checkup to ask some questions, and at another checkup in 6 months. You will be compensated for your time. Would you be interested in learning more?”

For those expressing interest, written informed consent will then be administered via the CRC in a quiet area of the clinic waiting room, or private room if available, during the same visit where baseline data collection and intervention will take place. The CRC will review the form in plain language, including details about inclusion/exclusion, aims, incentives, and that participation is voluntary.

Participants will receive a gift card valued at approximately \$25 as compensation for time and travel, with \$10 provided at enrollment (pre-) and \$15 provided at follow-up testing (post-), each taking place during normally scheduled well-child visits. All children will receive a new children’s book per standard ROR practice. Participants in the control arm will receive an additional, new, age-appropriate children’s book reinforcing screen-based media reduction (*Baby Unplugged: Play*), retail value \$7.99.

Study Advertisement: To optimize enrollment and reduce the burden of surprise for families being approached in the waiting room, a brief postcard developed by Reach Out

and Read will be distributed to eligible families at well-child visits immediately preceding those for of our study (i.e. at 4 month visit and 15 month visit, respectively). This will advise them that at their next visit, they may be eligible to participate in this study, describe the study in very general terms, and also note the financial incentive.

Inclusion and Exclusion Criteria: Accounting for a potential 10% attrition rate, at least 200 subjects with 100 in each age category is recommended for this study. We anticipate that 248 should be ample, given variation in effect sizes reported, uncertainty for those in younger children, and higher than usual attrition for this high-risk population.

Inclusion criteria for this study are:

- Gestation of at least 34 weeks,
- Age at initial screening 6 months (5.75 months-7.5 months) or 18 months old (17-21 months).
- No documented history of major neurological insult such as intracranial hemorrhage or V-P shunt.

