c) **Satisfaction with RS and frequency of use:** responses on surveys administered to caregivers at the 6-month follow up visit (12 or 24 months old) will be analyzed, including frequency and ease of use (e.g number of "push" notifications).

d) **Feasibility:** Caregiver satisfaction with RS will be conducted via closed and open-ended survey items administered via the CRC, including barriers to use (e.g. cell phone minutes, clinical flow, data plan), time of administration, and suggested means of improvement.

There are no safety endpoints involved with this study.

c) Procedures involved in the Human Research*

Randomization: Following agreeing to participate and providing informed consent, families in both age groups (infant and toddler) will be assigned to either the intervention or control cohort (62 in each cohort for each group) by research coordinators using a spreadsheet with assignment codes determined by computer-generated random numbers provided by a biostatistician (Group A and Group B). Participants will be blinded as to group assignment and not advised as to differences in intervention between groups, for the purposes of the research. The CRC will not be blinded, as this is infeasible. Statisticians will be blinded as to the definition of Group A or B (i.e. which is the intervention), to ensure objectivity in analyses.

Testing and Surveys: Testing and survey administration will be performed in a private part of the waiting area or clinic exam room, *in the following order of preference*, mindful of patient/clinic flow:

- 1) Before seeing the provider for the scheduled WCC.
- 2) After the provider has completed their exam, but before lab tests or shots.
- 3) After lab tests and shots, if needed.

Of note, all surveys and measures are administered to the parent (i.e. parent report), none directly administered to or involving the child.

At all times, deference will be given to clinic staff and the family to maintain the flow of the visit. The CRC will approach the clinic manager, supervising nurse, or clinical provider in charge of clinic flow on the morning of each clinic session, to discuss preferred strategies, including designated exam room for consent and survey administration. If unable to complete all data collection, the family will be free to go at their discretion and data collected will be utilized to the extent possible. The order of administration will prioritize items that are most important to achieve our study aims,

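### Families are assigned from a spreadsheet of codes, and nothing in the readable protocol hides the next code from the unblinded coordinator who recruits, consents and delivers both arms

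*Protocol*

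**What the plan says.** Section 8c (Randomization) places assignment after agreement and consent, with 62 families per arm in each age group, and has it done "by research coordinators using a spreadsheet with assignment codes determined by computer-generated random numbers provided by a biostatistician". The codes are Group A and Group B. Participants are not told how the groups differ, and the statisticians do not know which letter is the app. Of the coordinator the section says: "The CRC will not be blinded, as this is infeasible".

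The other relevant statements are spread over the protocol:

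- **Staffing (section 2).** A coordinator is listed at the Cincinnati centre, and "A primary research coordinator will be hired to conduct this study at the primary care clinical site in CT".
- **Recruitment (section 8a).** Children are found "via convenience sampling in the CHC@CCMC clinic waiting room". "The CRC will approach families in the waiting area, confirm that the child meets inclusion criteria by age".
- **Consent (section 15).** One CRC has sole responsibility for it.
- **Timing (section 8a).** Consent is taken "during the same visit where baseline data collection and intervention will take place".
- **Delivery (section 8c).** The CRC installs the app for one arm and goes over the screen-time book with the other.
- **Volume (sections 7 and 8a).** Full enrolment in 6 months is called feasible from "historical well-visit volumes for these ages (40/month meeting enrollment criteria").
- **Duration (section 5, Overview/Rationale).** "Our strategy is to conduct an innovative experiment that is achievable within 15 months".

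**The concern.** Random numbers protect a trial only if the person deciding who enters cannot know what the next number is. Here the protocol names the tool and the people who use it, but adds no step that hides later rows. Nearly every discretionary act between the waiting room and the intervention belongs to one person, who must know what A and B mean in order to deliver the arm.

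If that person could see the next code, knowledge of the arm could affect which families are approached, how the study is presented, and how the functional-literacy criterion is judged (section 8a defines it partly by the caregiver's ability to use the app). The arms could then differ in prognosis at entry. The planned ANCOVA on baseline LENA removes only the part of such a difference that the baseline score captures. The readable text also places baseline testing before the intervention, but not explicitly before assignment, so the covariate itself could be collected with the arm known.

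This is not a detail to leave to a statistical analysis plan, because the protocol itself fixes the assignment procedure.

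**Working it through.** **1. Does any readable statement conceal the next code?**

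| Statement | What it protects | Does it hide the next code? |
|---|---|---|
| Assignment follows consent (8c) | Order of steps | No. A list can be read before consent. |
| A/B labels (8c) | Blinding of the statisticians | No. The CRC delivers the arm and so knows the letters. |
| Participants not told of differences (8c) | Participant expectation | No. |
| REDCap (8d, 12, 19) | Data capture and storage | No allocation function is described. |
| Second coordinator in Cincinnati (2) | Possibly a separate holder of the list | No text gives that person the list or the release of codes. |

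Consent, baseline data and intervention share one visit, so the code is needed on the spot.

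**2. How much room is there to skip families?** The plan's own total is 62 x 2 arms x 2 age groups = 248. Visits come from the stated 40 per month.

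| Reading | Visits | Places | Not enrolled |
|---|---|---|---|
| Stated plan: 40/month, both ages together, 6 months | 40 x 6 = 240 | 248 | none (248/240 = 103%) |
| Same, enrolling the 200 that section 8a calls the recommended minimum | 240 | 200 | 1 - 200/240 = 17% |
| Recruitment for 9 months (assumed: 15 - 6 of follow-up) | 40 x 9 = 360 | 248 | 1 - 248/360 = 31% |
| 40 read as per age group (assumed) | 80 x 6 = 480 | 248 | 1 - 248/480 = 48% |

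The last column is an upper limit on selection, because families who refuse also use up visits. The 9-month row is generous: it leaves no time for set-up or analysis.

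**3. What would concealment buy?** Take one age group, n = 62 per arm, and assume the list is a random order of exactly 62+62. The protocol gives the totals but not the ordering method.

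- Readable list: 124 of 124 next arms known. Chance alone gives 62, so the excess is 62.
- Hidden list, with a CRC who tallies past arms and always guesses the one behind: expected correct = n + 0.5 x (2^(2n)/C(2n, n) - 1) = 62 + 0.5 x (2^124/C(124, 62) - 1) = 62 + 6.49 = 68.5, and 68.5/124 = 55%. A simulation of 20,000 lists gave 68.5.
- Reduction in excess: 1 - 6.49/62 = 0.895, about 90%.

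**4. Size of bias.** It depends on how often places would be steered, how different the steered families are, and how strongly baseline LENA predicts follow-up. The protocol gives none of these, so no figure is offered.

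**The case against.** The strongest reply is that the protocol is silent rather than wrong. It says neither who keeps the file nor that later rows are visible. Plural coordinators are mentioned, and the missing flow diagram of enrolment, consent and baseline testing might show a release step. This stands as a limit: a reader might infer that the CRC holds an open list, and the text does not say so. What remains is that the stated method does not prevent it.

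A reader might also infer that the CRC picks among eligible families. Section 8a describes screening from the daily clinic schedule, which is compatible with approaching everyone; convenience sampling merely leaves the choice open. This also stands. At the stated volume, every eligible visit would be needed and more, so systematic skipping would be hard to sustain. The influence of a known code on the presentation of the study or on consent does not need spare visits in the same way, but it too would slow enrolment.

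Finally, section 8b plans baseline comparisons between groups, and income, education and history of reading difficulty are collected. Gross selection on those might be noticed. Noticing it does not prevent or repair it, and differences in motivation would not show there. The exploratory, pilot character of the study lowers the stakes but does not alter the point.

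**Conclusion.** The point holds as a missing safeguard in a stated procedure, and should be fixed because the remedy is cheap and lost concealment cannot be restored in the analysis. Sections 8a, 8c and 15 together give one unblinded person recruitment, age eligibility, consent and delivery of both arms, and no readable text hides the next code from that person.

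The documents do not support the stronger conclusions that the list is open, that families will be selected by arm, or that the result will be biased by any particular amount. Under the plan's own volume there is little room to skip families; the room grows only if recruitment runs longer, fewer are enrolled, or 40 per month is per age group.

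The one quantity that can be given is predictability: 124 of 124 with a readable list against about 68.5 of 124 with a hidden one, assuming a random order of 62+62. Confidence is medium, chiefly because the flow diagram cannot be seen.

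**What to change.** In section 8c (Randomization), replace the description of the spreadsheet with a statement that:

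- the biostatistician loads the list, in A/B codes and stratified by age category, into a locked allocation function in the existing REDCap database or, failing that, prepares sequentially numbered, opaque, sealed envelopes;
- the CRC cannot view the list;
- one code is released at a time, only after eligibility and consent are recorded and baseline measures have been collected as far as that visit allows;
- siblings enrolled at the same visit receive one draw, since section 8a already requires them to share a group.

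Keeping A/B codes preserves the statisticians' blinding. The text should agree with the flow diagram. If enrolment has begun, the change can apply to the remaining allocations.

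The cost is small set-up work, or the preparation of envelopes, with no added visits or participants. Sibling pairs may cause slight departures from 62 per cell. Concealment will not be perfect: an unblinded CRC who tallies past arms can still guess slightly better than chance, about 55% under the assumption above.

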- Comfortable speaking English during their WCC and reviewing/comprehending study materials without a translator, including informed consent.
- Functional literacy in at least one primary caregiver, defined as the ability to navigate the RS application, read prompts provided by the RS application (targeted 6th grade reading level as estimated via the Readable.io website), and understand/provide informed consent, administered in English.
- Possession of a smartphone or tablet device capable of downloading, installing and utilizing the RS application.

Twins will be excluded from the study, to minimize confounding.

In the case of 2 eligible siblings presenting at the same visit (i.e. 6 month old and 18 month old), both may be enrolled, though will be randomized to the same group to minimize confusion and confounding.

In the case of an eligible sibling presenting after another sibling has been enrolled, this second child (and any other siblings) will be ineligible, to minimize confounding via a training effect.

b) Study Endpoints*

Outcomes of interest for this study (6 months post-intervention) are as follows:

a) **Descriptive Statistics:** Descriptive statistics will be used to summarize parent-child demographics, language and social-emotional testing scores (LENA Snapshot, DECA-I/T excerpted items), home reading environment/dialogic reading/cognitive-language attitudes (StimQ-P READ and PVR excerpted items, DialogPR-I/T), and screen time (ScreenQ). Group-wise comparisons will be performed to determine any differences

between randomization groups. Spearman's rank correlation will then be used to assess correlation between variables of interest at baseline and 6-month follow-up visits, applying age and gender as covariates.

b) **Pre-post intervention cognitive-behavioral outcomes:** Outcomes of interest will involve group-wise statistical comparisons pre-post intervention of language, social-emotional development, and home reading practices/attitudes measures. All repeated measures (LENA, DECA-I/T excerpted items, StimQ READ and PVR excerpted items, DialogPR, ScreenQ, reading attitudes) will be examined via paired t-test, Wilcoxon signed-rank test, and McNemar's tests. Association between home reading environment and screen time and language and social-emotional testing scores will be assessed by correlation coefficient and applied in general linear regression models, applying age and gender as covariates.

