a) Training in DRI: At the baseline well-child visit (approximately 6 or 18 months), the CRC will assist participating families in downloading and installing the RS app onto their mobile device, and briefly review its use. This is anticipated to take approximately 5-7 minutes. After downloading RS, the CRC will confirm that caregivers were able to open it, activate the videos, and address any questions. A postcard with simple, picture-based instructions (target 6th grade reading level) will also be provided, created by ROR. This handout/card will also convey contact information for the CRC in the event of a change in participant phone number or other contact information. Care will be taken to make the instruction process as brief as possible, to simulate how a pediatric provider or support staff would function in a busy, real-world clinical setting. The CRC will record administration time, qualitative feedback from families, and any major logistical concerns.

b) Rx for Success Application (RS): The RS mobile application (app) was developed by Children, Inc., available for free download via the iTunes or Android App stores (search term: Rx for Success). The app is designed to be informational and motivational with both video and cueing content. The app uses a “View It, Cue It, Do It” model that allows parents to quickly download the smartphone app (no iTunes or other account is needed, and installs on a variety of platforms), view brief videos of the age-indexed, research-based language enrichment practices; and regulate a text message cueing program. The app uses three motivational strategies in the cueing program: 1) Personalization; 2) Gamefication; and 3) Social media. Videos embedded in the RS app provide a summary of DR tailored for the child’s age, and suggestions for encouraging verbal interactivity and social-emotional engagement through dialogic reading. To achieve this, approximately 2 “push” notifications will be generated by the app per day

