Subjects will be approached as discretely as possible via a trained CRC in the clinic waiting area, and invited to discuss the study in an area that is as quiet and private as possible. For those expressing interest, written informed consent will be obtained in either a private area of the waiting room or in a private exam room, and all data will be collected in a private exam room. As this study involves minimal risk, initial discussion of the aims of the study or eligibility requirements in the waiting area does not represent a major risk to subject privacy, though the CRC will be advised to be as discreet as possible.

12) Provisions to maintain the confidentiality of data

Screening and survey data will be directly entered by the CRC into REDCap (www.REDCap.org), a secure, HIPAA-capable web-based data management tool, to the greatest degree possible (demographics and select parental surveys). All paper-based data will be transcribed into REDCap as expeditiously as possible. All subjects will be assigned a unique Study ID in REDCap, and at the conclusion of data collection for all subjects, all identifying information such as names and phone numbers will be deleted. Biostatisticians at Children Inc. and the principal investigator will only download deidentified data via REDCap for analysis, and then store this data on password-protected servers at their respective institutions (Children Inc. and CCHMC). REDCap data will be stored on secure, password-protected servers hosted by Cincinnati Children's Division of Biomedical Informatics, with state of the art security features. Hard copy records will be restricted to IRB-approved study personnel in locked cabinets at CHC@CCMC. Hardcopy data will be destroyed within 3 years of conclusion of the study.

13) Medical care and compensation for injury

This study involves minimal risk, and such provisions are not required.

14) Cost to subjects

There are no costs involved with participation in this research, other than use of smartphone data minutes using the RS application (if applicable; would not result in any cost in the case of increasingly common unlimited data plans), expected to be minimal. The RS application is completely free, with no special accounts needed.

15) Consent process

- Written informed consent will be administered via a trained CRC in a private section of the waiting area or private exam room at CHC@CCMC.

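### The protocol declares caregivers blinded to group assignment, but its own procedures reveal the assignment, and every efficacy outcome is their parent report

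*Protocol*

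**What the plan says.** **Masking (Protocol 8(c), Randomization).** For families: "Participants will be blinded as to group assignment and not advised as to differences in intervention between groups". For the coordinator: "The CRC will not be blinded, as this is infeasible". For the analysts: "Statisticians will be blinded as to the definition of Group A or B".

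**What each arm receives (Protocol 8(c), Dialogic Reading Intervention).** At the baseline visit "the CRC will assist participating families in downloading and installing the RS app onto their mobile device". The CRC also reviews its use and checks that it opens and the videos play. The app then issues about 2 push notifications a day. Control families receive an extra children's book on limiting screen media, which the CRC goes over with them briefly. No sham or comparison app is described.

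**What families learn beforehand.** Consent precedes assignment and covers eligibility and aims (8(a), Recruitment Methods). Two inclusion criteria refer to the RS application by name: the literacy criterion and the requirement for a device that can run it.

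**Outcomes (8(c), Testing and Surveys).** The protocol says that "all surveys and measures are administered to the parent (i.e. parent report), none directly administered to or involving the child". LENA Snapshot, the primary language measure on which the trial is powered, is among these.

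**Who collects them.** Sections 7 and 15 describe one full-time CRC. Section 12 says "Screening and survey data will be directly entered by the CRC into REDCap", then limits this to what is possible, naming demographics and some of the parental surveys, with paper records transcribed later.

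**The concern.** A caregiver who has been helped to install a reading app, and is then prompted by it daily, knows what she was given. A control caregiver who heard at consent that she needed a device able to run the app, and went home with a book, can work out what she was not given. The masking sentence thus claims a property that the design does not have.

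It matters because nothing downstream protects the outcomes. There is no direct test of the child, no objective measure and no blinded assessor. A caregiver who knows she was taught to read interactively may report more interactive reading, or more language, than she otherwise would. Exposure is greatest for DialogPR, whose content is what the app teaches. Bias probably favours the app for DialogPR, StimQ and LENA. For ScreenQ it could run either way, because limiting screens is the message of the control book. A reader who takes the masking sentence at face value would give the results more weight than unblinded self-report deserves.

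**Working it through.** **1. The claim against the procedures.**

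| Element | Intervention | Control |
|---|---|---|
| Given at baseline | App on own device, CRC-assisted | Screen-time book, reviewed by CRC |
| Between visits | About 2 push notifications a day | None described |
| Sham | None | None |
| App named in criteria reviewed at consent | Yes | Yes |

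Caregivers in both arms can identify what they received. The second half of the masking sentence (not being advised of differences) can be honoured; the first half cannot.

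**2. Who is masked.** Caregivers: no. CRC: no, as stated. Statisticians: yes, to the meaning of A and B. Masking the statisticians acts after the answers are recorded, so it leaves reporting bias untouched.

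**3. The plan's own sample size.** Inputs from 8(a): Cohen f = 0.30, power 80%, two-sided alpha 0.05, baseline covariate. With noncentral F, numerator df 1, two arms, one covariate and noncentrality f²N:
- N = 90 gives 0.09 × 90 = 8.1 on 1 and 87 df, power 0.804.
- Powering each of the two age categories separately: 2 × 90 = 180, the stated figure.
- With 10% attrition: 180 / 0.9 = 200, also as stated.

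The sample size is not in question here, and correcting the masking statement does not change it.

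**4. Illustration of the stake.** Assumed, not from the documents: reporting alone shifts the app arm by b SD; there is no true effect; baseline adjustment gives no variance reduction. Completers: 248 × 0.9 = 223, in two equal arms.

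z = b × √223 / 2, and P(reject) = Φ(z − 1.96) + Φ(−z − 1.96).
- b = 0.1: z = 0.75; 0.1125 + 0.0034 = 0.116, about 12%.
- b = 0.2: z = 1.49; 0.3204 + 0.0003 = 0.321, about 32%.

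**5. Range under other assumptions.**

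| Completers analysed | b = 0.1 | b = 0.2 |
|---|---|---|
| 90 (one age category) | 8% | 16% |
| 180 | 10% | 27% |
| 180, assumed pre-post correlation 0.5 | 12% | 34% |
| 248 (no attrition) | 12% | 35% |

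A larger sample or a better-predicting baseline raises the false-positive rate, because bias does not shrink as precision improves. For scale, f = 0.30 corresponds to d = 0.6 with two equal groups, so shifts of 0.1 and 0.2 SD are one-sixth and one-third of the planned effect.

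**The case against.** The strongest reply is that the masking sentence qualifies itself. Its second half suggests that what was meant is masking to the contrast between arms. A neutral recruitment script and a control book that the CRC also reviews support that reading. The protocol is open about the unblinded CRC and about parent report, and it calls itself exploratory and a pilot. This softens the intent but does not rescue the words: blinding to group assignment is stated and cannot occur.

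Several stronger readings are tempting and are not supported:

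- **That families are masked to the hypothesis.** A reader might infer this as what remains. No section says so. The CRC presents the aims at recruitment and again at consent, and the consent form is not among the documents.
- **That the protocol states the CRC collects the follow-up outcomes.** It does so explicitly only for the satisfaction survey. For the efficacy measures it is an inference from single-CRC staffing, a reasonable one, but the Randomization paragraph uses the plural for coordinators and section 12 does not say that LENA or DialogPR answers are keyed live by the CRC.
- **That literacy criteria make self-completion available to everyone.** The criterion is "Functional literacy in at least one primary caregiver", who need not be the one attending. The baseline survey itself asks about a history of dyslexia or functional illiteracy, no reading level is given for LENA, and the open-ended favourite-activities item still needs someone to code it.
- **That self-completion would cure the bias.** It reduces interviewer influence only. The caregiver still knows she has the app.
- **That false-positive rates of 12% or 32% are estimates for this trial.** The shifts are assumed.

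On order of administration, section 8(c) already prioritises StimQ, LENA and DECA, and mentions the app-use survey after the repeated measures. It does not, however, fix that the survey comes last or that the app is not discussed first.

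**Conclusion.** The masking statement is wrong as written. Caregivers cannot be blinded to group assignment under the protocol's own procedures; at most they are not advised of the differences between arms. Every efficacy outcome, including the primary one, is therefore unblinded parent report, probably gathered by the person who delivered the intervention, although the protocol leaves that last point implicit.

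If reporting shifted by 0.1 to 0.2 SD, the two-sided rejection rate with no true effect would be about 12% to 32% with 223 completers, against 5%. This rests on an assumed shift, 10% attrition, pooled age categories and no credit for baseline. The direction probably favours the app on DialogPR, StimQ and LENA and is uncertain on ScreenQ. The point does not invalidate the trial or its sample size; it limits what a positive result can be said to show. It should be corrected.

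**What to change.** 1. **Restate masking in 8(c).** Caregivers and the CRC know which intervention was received; caregivers are only not advised of the differences between arms; only the statisticians are masked. Claim masking to the hypothesis only if the consent form supports it.
2. **Carry this into the conclusions.** Describe all efficacy results, the primary one included, as unblinded parent report.
3. **Fix the order at follow-up.** Complete every outcome measure before any discussion of the app, and give the RS-use survey last.
4. **Offer self-entry.** Where the attending caregiver is able, let her enter the closed-ended measures directly in REDCap, in the same way in both arms, with CRC help on request.

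Items 1 to 3 are changes of wording and sequence and cost almost nothing. Item 4 uses a system already in place but may lose a few items to skipping, and the protocol mentions no study tablet, so a device has to be arranged. It lessens interviewer influence, not the caregiver's own desirability bias, so items 1 and 2 are needed whether or not it is adopted.
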